### Rules for Rescheduling Treatment Session

- 1) Participant reports taking CNS stimulants (non-amphetamine/methylphenidate and/or amphetamine-based stimulants), but express willingness to discontinue CNS stimulants to enable continued study participation
- 2) Subject reports sleep disruption and epileptologists determine that iTBS should not be provided during scheduled visit, but could be provided after sufficient sleep is achieved.

To prevent equipment malfunction, the equipment will be inspected before and after each iTBS session. Manufacturer guidelines will be followed according to maintenance and useful life of the device. Should any equipment appear broken or have loss of integrity, the equipment will not be used until it is inspected by the biomedical engineering department at Hines VA Hospital and the Magventure service representatives.

[name] [name] has secured an FDA Investigational Device Exemption (#G150119) for the intended use of this device (Magventure MagPro X100) for persons with mild TBI. Safety protocols and total amount of stimulation are the same as the currently approved FDA IDE. An FDA Investigational Device Exemption has been secured dated 1.12.2022., G210364. The FDA has found that iTBS does not present a risk to the health, safety, or welfare of individuals with brain injuries, and does not cause seizures at a rate of stimulation used in the current research design for persons without brain injury. However, it is noted that the risk of causing a seizure in persons with brain injuries or ischemic stroke is not known but it is possible that iTBS could cause one or more seizures.

In event of a seizure, the following response will be administered:

- Within 0-5 Minutes: Stabilization phase, initiated immediately upon patient demonstrating seizure-like activity
  - Stop stimulation
  - Notify RRT (Rapid response team) and MD experienced in seizure management
  - Basic Seizure First Aid will be provided by research staff until RRT arrives:
    - Ensure patient in safe position
    - Stabilize patient (airway, circulation, breathing, neurologic exam)
    - Track time
    - Obtain vital signs (BP, HR, RR and SpO2)
    - Vast majority of seizures are self-limited within 5 minutes1
- Within 5-20 minutes: Initial therapy phase
  - RRT arrives within 5-10 minutes of seizure onset and assumes responsibility for carrying out all emergency procedures. Research team will notify RRT of intervention and patient's vital signs thus far to facilitate coordination of care. RRT initiates the tasks below; the time frame for these tasks may run into next phase.
    - O2 administration if SpO2 <90%
    - Cardiac monitoring
    - Glucose assessment
  - MD will assess the situation and prescribed benzodiazepine will be administered by RRT if indicated. Respiratory support will be provided by RRT if necessary.
- Within 20-40 minutes-Second therapy phase

- Emergency medical services continues individualized care.
- Following termination of seizure activity, medical evaluation completed by emergency room physician, [name], covering MD or on call Epilepsy physician

RRT will determine timing of transportation to ER once subject is determined to be stable for transport.

The stimulating coil will be used on multiple Veterans. To prevent the spread of contamination from one Veteran to the next, the coil will be disinfected and sanitized after every iTBS session.

To further ensure participant safety, all female Veterans will submit to a urine pregnancy screen at baseline. If the urine screen is positive for pregnancy, the Veteran will be excluded from participation.

To prevent injury during participation in AMPS assessment, all Veterans will be supervised by an AMPS certified Occupational Therapist.

*Psychological:* If the participant exhibits frustration or fatigue, then the response plan is to pause testing and comfort them. Testing will be resumed after the Veteran exhibits signs of reduced frustration. Should the Veteran experience PTSD symptom trigger during any treatment or testing, the response plan will be to immediately consult with the Hines Mental Health Service and follow their recommendation.

*To monitor depression*, specifically suicide ideation, the C-SSRS will be administered at baseline and repeated as part of each battery assessment. Administration of the C-SSRS will be as defined:

- At each C-SSRS administration, all participants will complete the first two questions, #1 'wish to be dead' and # 2 non-specific active suicidal thoughts'
- For participants answering questions 1 and 2 affirmatively, then researchers will administer the entire C-SSRS and
  - For Lifetime: If the C-SSRS results indicate that a participant endorses having had suicidal ideation or a suicide attempt in the past, then the participant will be asked if their mental health provider(s) are aware of this.
    - If provider(s) are aware, and patient denies all suicidal ideation/behavior at the present time (i.e., past month), participant will be allowed to proceed in the study.
    - If the participant is not actively engaged in mental health treatment, then the research psychiatrist will be contacted to determine what form of psychiatric care is warranted at this time (e.g., contacting of emergency authorities, escorting participant to intake for scheduling an outpatient evaluation).
    - If they are engaged in mental health treatment and their mental health providers are not aware of past suicidality, then researchers will inform the mental health provider(s) of past suicidality and the determination of study eligibility will be made based on the recommendations of these mental health providers
  - For Past Month: If at any point during the C-SSRS subject endorses passive suicidal ideation at the present time (wish to be dead in past month), then:
    - The study team's psychiatrist will be contacted to evaluate subject symptom acuity, and:

- If the participant is actively engaged in mental health treatment, then the study team's psychiatrist will discuss the case with the participant's mental health provider who will determine the safety of subject continuing in the study.
- If the participant is not actively engaged in mental health treatment, then the research psychiatrist determine what form of psychiatric care is warranted at this time (e.g., contacting of emergency authorities, escorting participant to intake for scheduling an outpatient evaluation).

If subject endorses any active suicidal ideation (C-SSRS questions 3 through 5) OR recent suicidal behavior (i.e., preparatory behaviors, self-harm, recent suicide attempt) subject will be excluded from study AND study team psychiatrist will be contacted to evaluate subject and determine what form of urgent psychiatric care is warranted at this time (e.g., contacting of emergency authorities, contacting of subject's mental health provider(s)).

*fMRI:* Prior to enrollment into the study, prescreening is completed with research staff to evaluate the Veteran's compatibility and safety for having an MRI related to the presence of ferromagnetic material in the body (i.e. metal fragments in brain/skull, metal surgical clips, etc). Prior to the MRI, the MRI safety checklist is repeated (from screening) and reviewed for contraindications. Some people have been noted to be anxious or claustrophobic during the scan. In the pre-screening process, it is asked and reviewed if the Veteran has any issues with claustrophobia or anxiety in closed spaces. The Veteran may be recommended to not participate in the study if it is unknown. The MRI scanner makes loud banging noises while taking a measurement, so either ear plugs, or specially designed headphones will be used to reduce the noise. The researchers will be in communication with the participant through an intercom system to ask how the participant is doing. The earplugs should not get in the way of communicating with the researchers. The participant can speak to the technician by talking out loud. If at any time, or for any reason, the participant wishes to stop the exam, he may do so by squeezing a rubber ball.

This protocol will involve the vulnerable population of persons with cognitive disabilities and may involve persons lacking decisional capacity. Due to the nature of the medical condition of the Veterans recruited, the healthcare surrogate (legally authorized representative) may be the person providing informed consent for research participation. All Veterans will provide assent in addition to the informed consent if necessary to obtain consent from the healthcare surrogate. In order to develop treatments to improve cognitive function, individuals with cognitive impairment related to ischemic stroke or TBI must participate in the current study design.

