**Rules for Pausing treatment to Evaluate Need to Change iTBS Treatment Protocol:**

- 1) Any seizure
- 2) Skin break-down on scalp at site of TMS
- 3) Constant headaches that do not resolve with acetaminophen
- 4) Suicidality response on C-SSRS is 2 or higher
- 5) A composite score of visuomotor processing speed assessments that falls below 2 standard deviations from the mean.

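### Read literally, the C-SSRS instruction does not require a participant who affirms only one of items 1 and 2 to be asked the items that decide exclusion and urgent psychiatric evaluation

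*Combined protocol and SAP*

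**What the plan says.** The relevant text is in section 5.1 of the combined protocol and SAP.

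Under Protection Against Risk (Psychological), "the C-SSRS will be administered at baseline and repeated as part of each battery assessment". At each administration everyone answers item 1 (wish to be dead) and item 2 ("non-specific active suicidal thoughts"). The next step is: "For participants answering questions 1 and 2 affirmatively, then researchers will administer the entire C-SSRS".

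Three response rules are printed beneath that sentence:

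- **Lifetime.** This begins "If the C-SSRS results indicate that a participant endorses having had suicidal ideation or a suicide attempt in the past" and asks whether the mental health providers know. If they know, and the "patient denies all suicidal ideation/behavior at the present time (i.e., past month), participant will be allowed to proceed in the study". For someone outside care: "If the participant is not actively engaged in mental health treatment, then the research psychiatrist will be contacted". Providers who are unaware are to be told.
- **Past Month.** The study psychiatrist is contacted for passive ideation, defined as a wish to be dead in the past month.
- **Exclusion and urgent care.** This is triggered by items 3 to 5 or by recent suicidal behaviour.

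Separately, the list headed "Rules for Pausing treatment to Evaluate Need to Change iTBS Treatment Protocol" includes: "Suicidality response on C-SSRS is 2 or higher".

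**The concern.** The exclusion and urgent-care rule can act only on answers that have been collected. If the full scale follows only when both screening items are affirmed, a participant who affirms one of them can leave the assessment without being asked the questions on which that rule depends.

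The case of most concern is item 1 denied and item 2 affirmed. The protocol itself describes item 2 as active suicidal thoughts. Yet it falls between the two current-ideation rules: the Past Month rule names only the passive item, and the exclusion rule specifies items 3 to 5. Staff following the text would not learn whether this participant meets the protocol's own criterion for exclusion and urgent evaluation.

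**Working it through.** The plan gives no figure to reproduce. The check sets the four possible answer patterns against the rules in section 5.1, taking the pause rule's threshold as item or level 2.

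| Item 1 | Item 2 | Full scale required (literal reading) | Pause rule met through item 2 | Items 3–5 and behaviour required to be asked | Item 1 available to trigger Past Month contact |
|---|---|---|---|---|---|
| no | no | no | no | no | no |
| yes | no | no | no | no | yes |
| no | yes | no | yes | no | no |
| yes | yes | yes | yes | yes | yes |

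1. **No/no.** This is the ordinary purpose of a short screen and is not at issue.
2. **Yes/no.** The Past Month rule can reach this participant if it is taken to apply despite being printed under the both-items condition. Recent suicidal behaviour, an exclusion trigger in its own right, need not be asked.
3. **No/yes.** iTBS is paused, but the remaining items need not be asked and the Past Month rule is not triggered. The heading of the pause list gives its purpose as reviewing the iTBS protocol. Neither a psychiatric evaluation nor completion of the scale is specified.
4. **Yes/yes.** All rules work as intended.

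**The Lifetime rule as cover for no/yes.** It is printed under the same condition, so on a strict reading it is not reached. On a generous reading it leads to the psychiatrist when the participant is not in care, and to the providers when they are unaware. When the participant is in care and the providers already know, it names no contact: the line allowing the participant to proceed requires denial of all past-month ideation, which this participant has not given. On neither reading does it collect items 3 to 5.

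**The same check if either item was meant.** Patterns 2 and 3 now receive the full scale, so items 3 to 5 and behaviour are asked. Suppose a no/yes participant affirms item 2 for the past month and denies everything further. The exclusion rule is not met and the Past Month rule is still not met, because it names item 1 only. That part of the gap does not depend on how the opening sentence is read.

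**Time cost.** Table 2 in section 5.5 lists 0.1 h per C-SSRS: 0.1 × 60 = 6 minutes. The table does not say whether this covers the full scale or only the two screening items, so treating it as the added time is an assumption.

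**The case against.** The strongest reply is that the sentence is loosely worded and that either item was meant. It says neither both nor only. A separate tier for passive ideation alone makes little sense beneath a condition that already requires active thoughts. This is a fair reading and may well be the intended one. It would close the gap for items 3 to 5, but the text does not say so, and past-month item 2 would still have no past-month contact named.

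A second reply is that the pause rule's threshold of 2 is not defined as an item, a level or a score, and Table 2 lists the C-SSRS as a raw score. That stands as a caveat. If 2 were a count of affirmed items, no/yes would score 1 and would not pause treatment. The uncollected items would remain uncollected, and the one response that the natural reading provides would be lost.

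A reader might infer that the protocol lets a participant with active suicidal thoughts continue stimulation unassessed, or that no psychiatric route exists. The documents do not support this. On the natural reading treatment is paused, and on Study-Days 2 and 3 the first test battery precedes iTBS, so stimulation would be held. The Lifetime rule may bring in a psychiatrist or provider. Staff are free to ask more, and section 5.7 lets the investigator withdraw a participant for safety. None of these, however, requires the missing items to be asked.

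**Conclusion.** The point holds as a wording defect in a safety rule and should be fixed. Followed literally, the instruction does not require items 3 to 5 or recent behaviour to be asked of a participant who affirms only one screening item. Under either reading, the Past Month rule omits item 2.

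The conclusion about collecting the remaining items rests on the literal sense of the opening sentence. The conclusion that no/yes pauses iTBS rests on taking 2 as item or level 2. The frequency of single-item answers is not given and is probably low in a pilot of 48, so the table describes the rules and not how many participants are affected. Nothing shows that the sponsor deliberately chose to skip these questions. Endpoints, sample size, power and alpha are unaffected.

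**What to change.** Make two edits in section 5.1, Protection Against Risk (Psychological):

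- In the sentence that opens the full scale, replace *questions 1 and 2* with *question 1 or question 2*. Opening it on item 2 alone would not be enough, because a participant who affirms only item 1 would still not be asked about recent suicidal behaviour.
- In the Past Month rule, add past-month item 2 as a trigger for contacting the study psychiatrist, and state that the rule applies whether or not the full scale was given.

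The pause rule can stay, although stating that 2 means item or level 2 would remove the remaining doubt. The cost is about 6 minutes per affected administration, under the assumption above, and possibly a few more psychiatrist contacts.

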## 5.2 Recruitment Methods

48 Veterans will be enrolled.

We will identify a cohort of Veterans from the corporate data warehouse (CDW) by using the ICD codes in the national inpatient and outpatient files available with VA Informatics and Computing Infrastructure. We will identify Veterans with ischemic stroke or TBI admitted to a rehabilitation bed and/or seeking outpatient rehabilitation services (i.e. OT, SLP) from Hines VA in the previous 10 years. We will filter and sort this list to exclude primary diagnoses other than ischemic stroke or TBI, any dementia diagnoses, deaths and enrollment in extended care. We will then re-sort the list by primary and co-occurring diagnoses, gender, age, date of most recent neurologic event, comorbid medical conditions including seizure disorders, by last date of a VA rehabilitation service, and by prescribed medications (by first and last fill date as well as dose). Once a list of possible participants is generated, a chart review encompassing CPRS, JVL and

CAPRI will be conducted to review for pre-screening of eligibility, including, but not limited to, medication (and recent changes (and recent inpatient services for medical stability. We will use the sorted list to minimize heterogeneity by excluding Veterans with both ischemic stroke **and** TBI, receiving anti-epileptic medications to control seizures or have a documented seizure three months prior to list extraction, and Veterans with these comorbid medical conditions: congestive heart failure, implanted pacemakers, defibrillators and/or cochlear implants. We anticipate having at least 1,500 Veterans remaining on the list from which we will randomly sample 500 males (250 with ischemic stroke, 250 with TBI) who will each be sent recruitment letters. We anticipate a smaller percentage of female Veterans on the list, therefore we will send a recruitment letter to all female Veterans to reduce risk of results being non-representative across biological sex. The letter will introduce the study and inform Veterans that researchers will be contacting them by telephone, text, and/or email to determine study participation interest. Veterans will be contacted up to 5 times. To determine interest in study participation, male Veterans will be contacted according to the order of the randomized list. During telephone contact, male Veterans expressing interest in study participation will continue with the telephone call to start screening. All female Veterans will be contacted and those expressing interest, will also continue with the telephone call to start screening.

A flyer will be created to provide to VA clinicians to provide to potential candidates or caregivers and post in approved common areas. We will also screen medical records of Veterans in relevant clinics, such as Neurology, which will be accessed through CPRS.

Veterans will receive \$100 compensation for completed participation in the study protocol. Compensation will be disbursed via Electronic Funds Transfer (EFT) using the veteran's preferred method (ex. Direct Deposit or Direct Express Debit card, etc.). Veterans who are unable to utilize this option may not be able to receive compensation. Participants will have an opportunity to discuss this option prior to consenting to participate in the study. The participant will be advised payment will take up to 10-14 days to show on their provided account.

There is no additional compensation for participation in the optional study treatments.

Parking vouchers will be provided at the time of visit to Northwestern University CTI. As long as participant parks in designated Northwestern Memorial parking garage, they will receive a voucher for the parking. Map and directions to the appropriate lot will be provided prior to the appointment.

### **5.3 Informed Consent Procedures**

No informed consent waivers will be obtained.

A partial HIPAA waiver will be requested for recruitment and initial screening.

The consent process will be conducted in English by trained research staff at Hines VA in a designated, private treatment room. Because some of the assessments used are currently only validated in English, the Veteran, and as necessary, the healthcare surrogate must be fluent in written and verbal English. If either of these individuals cannot speak English, the Veteran will be excluded from the study. The Principal Investigator will be available for further discussion or questions regarding research participation as needed during the informed consent meeting.

Informed consent documents will be made available to potential participants, and as applicable the healthcare surrogate, prior to the informed consent meeting. Research participants have

access to research staff to assist with any questions or concerns until understanding is achieved to the judgment of the individual asking the question. If a potential participant refuses, no further contact will be made. If the Veteran, or healthcare surrogate with assent of the Veteran, consents to the study, a copy of the signed consent is provided, a copy is filed with the Hines IRB, and the original Informed Consent is placed in a research binder and maintained in a locked file cabinet at Hines VA. Once the informed consent process is completed, a note will be documented in CPRS (Hines Electronic medical record system) and the Veteran will be flagged as a research participant.

The optional study procedures will be included in the informed consent, if the participant is eligible to participate in the optional procedures, the researcher will provide information about the additional treatment sessions. The participants will initial their assent or dissent to participation in the optional study treatments. It will be communicated in the informed consent process that they can change their mind in participation of the additional treatments and participation at any time. If they chose to opt out of the participation, documentation will be made in the participants study binder and CPRS. If they chose to opt in after initially declining, a new Informed consent will be signed and dated, and documentation will be made in participants study binder and CPRS. Participation in the optional study procedures will not have impact in the participation in the primary study.

**Northwestern Specific Procedures:** All participants will sign a Northwestern IRB approved consent form and a VA approved consent acknowledging participation in a VA sponsored study. Copies of the Northwestern signed consent forms and original VA consent forms will be mailed via chain of mail custody to the Clinical Research Coordinator at the Hines VA. Copies of the VA consent will be provided to the Hines IRB. Consent documents will be stored in locked file cabinet, behind a locked door at the Hines VA Building 1, Room B317. A copy of the signed Northwestern consent form will be provided to NU through the Study Tracker system.

